#### **Trial Design:**

This is a phase I, randomized, placebo-controlled, observer-blind, safety and immunogenicity study of SARS-CoV-2 mRNA vaccine (BNT162b1) in Chinese healthy subjects. After randomization, the trial for each subject will last for approximately 12 months. Screening period is 2 weeks prior to randomization (Day -14 to Day 0), and each dose of either SARS-CoV-2 vaccine (BNT162b1) or placebo will be given intramuscularly (IM) on Day 1 and on Day 22. After each age group completes the follow-up 28 days after boost vaccination (Day 50), initial analysis will be conducted.

Subjects who are  $\ge$ 18 years old and  $\le$  55 years old will be enrolled in adult group, and healthy elderly subjects who are  $\ge$ 65 years old and  $\le$ 85 years old will be enrolled in elderly group. Approximately 72 subjects for each age group will be allocated to three cohorts (BNT162b1 high-, low-dose groups and placebo group) in parallel, with approximately 24 subjects at each BNT162b1 dose level, including 24 placebo group subjects, the subjects will be randomized in a 1:1:1 ratio.

After the 14-day safety observation post the prime vaccination of the subjects in adult group, the prime vaccination for the subjects in the elderly group will start. SRC will review the available safety and tolerability data of all subjects in a cohort (including safety observation 14 days after the prime vaccination for all subjects in this cohort) before starting the boost vaccination for each cohort, to decide whether the BNT162b1 vaccine can be boosted.

For dose allocation design, see schematic diagram in **Figure 1**. For the planned assessments and visits, see schedule of activities in **Table 2**.

#### **Subjects enrollment and dose cohorts:**

The study will be aimed at enrolling SARS-CoV-2 naïve subjects. All subjects who sign the informed consent form (ICF) and have confirmed basic eligibility at Screening will be tested for SARS-CoV-2 antibodies (qualitative), virus nucleic acid and chest computed tomography (CT). Within 2 weeks after the screening visit, naïve subjects selected in each cohort at Screening will be randomized at visit 1.

The study will follow a parallel dose cohort design, as shown in **Figure 1**.

The enrollment process of subjects in adult group is as follows:

- The planned low-dose cohort, high-dose cohort and placebo group. 72 subjects will be randomized in a 1:1:1 ratio to inject BNT162b1 or placebo on Day 1.
- If the SRC considers that the subjects are safe with good tolerance after 14 days of observation, boost vaccination will be conducted on Day 22.
- When the subjects in the adult group completed safety visits up to 14 days post prime vaccination, the available safety data for all subjects were summarized. If approved by the SRC,
  - The planned dose cohorts of elderly group will be initiated (see Figure 1).
     The data assessed by the SRC comprises: vital signs, TEAEs, local reactions, blood/clinical laboratory data and brief physical examination outcome.
  - O The parallel dose cohort study is conducted in the elderly group with consistent methods as those in the adult group (see **Figure 1**).

#### Vaccination protocol and visit schedule

Each randomized subject will be given two doses of either BNT162b1 (10 or 30 μg) or placebo intramuscularly (IM) – one vaccination at Visit 1 (on Day 1) and one vaccination at Visit 5 (on Day 22), into one third of the deltoid muscle, preferably in the non-dominant arm.

From the treatment randomization, each subject will be required to attend 12 clinical visits:

All immunized subjects will attend Visit 1 (prime vaccination) on Day 1, Visit 2 on Day 2 (24 hours after prime vaccination), Visit 3 on Day 8 (7 days after prime vaccination), Visit 4 on Day 15 (14 days after prime vaccination), Visit 5 on Day 22 (boost vaccination), Visit 6 on Day 29 (7 days after boost vaccination), Visit 7 on Day 36 (14 days after boost vaccination), Visit 8 on Day 43 (21 days after boost vaccination), Visit 9 on Day 50 (28 days after boost vaccination), Visit 10 at Month 3, Visit 11 at Month 6 and Visit 12 at Month 12.

Blood samples of subjects in adult group will be collected at the following visits for different tests: at Screening Visit (Visit 0) for eligibility screening tests (including clinical laboratory), at Visits 2, 3, 6 for routine safety laboratory testing (visits 2, 6 coagulation function test, visit 2, 6, 11 thyroid function test), at Visit 1 (prior to prime vaccination) and Visits 5 (prior to boost vaccination), 6, 8, 10, 11, 12 for humoral immunity (antibody). Blood sample will be collected at Visit 1 (prior to prime vaccination) and Visits 6, 8, 11 for cell-mediated immunity (CMI). Urine samples will be collected at Screening Visit (Visit 0) for eligibility screening and collected at Visits 2, 3, 6 for regular safety laboratory testing; serum samples of women of childbearing potential will be collected at Screening Visits (Visit 0) and Visit 5 (prior to boost vaccination) for pregnancy test. Fingertip blood will be collected during the screening visit (visit 0) for detection of SARS-CoV-2 antibody and HIV antibody.

Blood samples of subjects in elderly group will be collected at the following site visit for different tests: at Screening Visit (Visit 0) for eligibility screening tests (including clinical laboratory), at Visits 2, 3, 6 for regular safety laboratory testing, at Visit 1 (prior to prime vaccination) and Visit 5 (prior to boost vaccination), 6, 8, 11, 12 for humoral immunity (antibody). Blood sample will be collected at Visit 1 (prior to prime vaccination) and Visit 6 for cell-mediated immunity (CMI). Urine samples will be collected at Screening Visit (Visit 0) for eligibility screening and collected at Visits 2, 3, 6 for regular safety laboratory testing; serum samples of women

of childbearing potential will be collected at Screening Visits (Visit 0) and Visit 5 for pregnancy test. Fingertip blood will be collected during the screening visit (visit 0) for detection of SARS-CoV-2 antibody and HIV antibody.

Each subject will receive diary cards to collect solicited reaction for 14 days after each vaccination (including the days of vaccine/placebo vaccination), and unsolicited AE for 21 days after prime vaccination and 28 days after boost vaccination (including the days of vaccine/placebo vaccination). Additional safety assessments will include vaccine related adverse events (AEs) collection for the rest of the entire trial.

[figure not shown]
# Primary objective

• To evaluate the safety and tolerability profiles of BNT162b1 prime/boost (P/B) immunization given 21 days apart from different doses in SARS-CoV-2 naïve Chinese healthy subjects through 28 days after boost vaccination.

## **Secondary objectives**

- To observe the immunogenicity (anti-S1 and anti-RBD IgG antibody) of two doses of BNT162b1 given 21 days apart measured by enzyme-linked immunosorbent assay (ELISA).
- To observe the immunoreactivity of healthy subjects after BNT162b1 P/B immunization by the true virus-based SARS-CoV-2 neutralizing antibody assay.
- To observe the safety of BNT162b1 vaccination in Chinese healthy subjects until the end of the study.
- To conduct 12-month follow-up for healthy subjects in the BNT162b1 vaccination dose cohorts, and observe the sustainability of the immune response to BNT162b1.

#### **Exploratory objective**

#### **Subject subjects:**

**Healthy subjects:** SARS-CoV-2 naïve

**Planned age range:** Adults (age  $\ge$ 18 and  $\le$ 55 years old) and elderly (age  $\ge$ 65 years old and  $\le$ 85 years old)

**Planned subjects:** a total of 144 subjects will be randomized, including approximately 72 in each of 2 age groups (including 2 dose cohorts and 1 placobo group, 24 in each group).

#### **Planned number of cohorts:**

Subjects will be allocated to receive 2 BNT162b1 dose cohorts or placebo group (in each group: n=24 subjects).

- Cohort 1: BNT162b1 low-dose;
- Cohort 2: BNT162b1 high-dose;
- Cohort 3: placebo.

# For adult subjects (age $\geq$ 18 and $\leq$ 55)

#### **Inclusion criteria:**

1. Male or female subjects of  $\geq$ 18 years old and  $\leq$ 55 years old with body mass index (BMI)  $\geq$ 18 and  $\leq$ 30 at the Screening Visit.

- 2. Individuals who are in good health condition at the time of entry into the trial as determined by medical history, physical examination (including vital signs, ECG) and eligibility screening test (hematology, blood chemistry and urine analysis) and clinical judgment of the investigator at Screening Visit.
- 3. The subject can provide with informed consent and signs and dates a written informed consent form (ICF) prior to the initiation of any trial procedures.
- 4. They must be able to understand and follow trial-related instructions.
- 5. They must be willing and able to comply with planned visits, treatment schedule, laboratory tests and other requirements of the trial.
- 6. Negative in antibodies screening of SARS-CoV-2 (fingerstick).
- 7. Normal in chest CT scans (no imaging features of COVID-19).
- 8. Axillary temperature  $\leq 37.0^{\circ}$  C.
- 9. Negative SARS-CoV-2 test in throat swabs by RT-PCR.
- 10. Women of childbearing potential (WOCBP) must have a negative beta-human chorionic gonadotropin (β-hCG) in serum sample at Screening Visit. Women that are postmenopausal (Menopause ≥ 12 consecutive months) or permanently sterilized will be considered as not having reproductive potential.
- 11. WOCBP must have used effective contraception 14 days prior to screening and agree to use effective contraception continuously during the trial period, from 14 days prior to Screening Visit to 60 days after the last immunization.
- 12. WOCBP must agree not to donate eggs (ova, oocytes) for the purposes of assisted reproduction during trial, starting from Screening Visit and continuously until 60 days after be given the last immunization.
- 13. Men who are sexually active with a WOCBP and have not had a vasectomy must agree to practice a effective form of contraception with their female partner of childbearing potential during the trial, starting from Screening Visit and continuously until 60 days after be given the last immunization.
- 14. Men must be willing to refrain from sperm donation, starting from Screening Visit and continuously until 60 days after receiving the last immunization.

#### **Exclusion criteria:**

- 1. Have had any acute illness, as determined by the investigator, with or without fever, within 72 h prior to the prime vaccination. An acute illness which is nearly resolved with only minor residual symptoms remaining is allowable if, in the opinion of the investigator, the residual symptoms will not compromise their well-being if they participate as trial subjects in the trial, or that could prevent, limit, or confound the protocol-specified assessments.
- 2. Are breastfeeding on the day of Screening Visit or who plan to breastfeed during the trial, starting from Screening Visit and continuously until at least 90 days after the last immunization. Women or partners who plan to become pregnant within 1 year post the screening visit.
- 3. Have a known allergy, hypersensitivity, or intolerance to the planned vaccine for trial including any excipients.
- 4. Used to have a history of hypersensitivity or serious reactions to vaccination.
- 5. Received any vaccination within 4 weeks prior to Visit 1.
- 6. Don't agree to not be vaccinated during the trial, starting from Screening Visit and continuously until 28 days after receiving the last immunization, except emergency vaccination (e.g. rabies vaccine, tetanus vaccine).
- 7. Had any medical condition (e.g., autoimmune disease) or any major surgery (e.g., requiring general

- anesthesia) within the past 5 years, which in the opinion of the investigator, could compromise their well-being if they participate as trial subjects in the trial, or that could prevent, limit, or confound the protocol-specified assessments.
- 8. Have any surgery planned during the trial, starting from Screening Visit and continuously until at least 90 days after the last immunization.
- 9. Had any chronic use (more than 14 continuous days) of any systemic medications that affects immune function, including immunosuppressant or other immune-modifying drugs, within 6 months prior to Screening Visit unless in the opinion of the investigator, the medication would not prevent, limit, or confound the protocol-specified assessments or could compromise safety of subjects.
- 10. Had administration of any immunoglobulins and/or any blood products within the 3 months prior to Screening Visit.
- 11. Had administration of another investigational product including vaccines within 60 days or 5 half-lives (whichever is longer), prior to Screening Visit.
- 12. With known history of AIDS or HIV test positive.
- 13. History of HBV or HCV infection, through medical inquiry.
- 14. History of SARS, SARS-CoV-2 or MERS infection. Suspected SARS patients should be screened for SARS antibodies.
- 15. Previously participated in a clinical trial involving lipid nanoparticles.
- 16. Are subject to exclusion periods of other clinical trials or simultaneous participation in another clinical trial.
- 17. Have any affiliation with the study site (e.g., are close relative of the investigator or dependent person, such as an employee or student of the study site).
- 18. Have a history of drug abuse or known medical, psychological, or social conditions within the past 5 years. In the opinion of the investigator, could comprise their well-being if they participate as trial subjects in the trial, or that could prevent, limit, or confound the protocol-specified assessments.
- 19. Have a history of narcolepsy.
- 20. Have history of alcohol abuse or drug addiction within 1 year prior to Screening Visit.
- 21. Have a history of or suspected immunosuppressive condition, acquired or congenital, as determined by medical history and/or physical examination at Screening Visit.
- 22. Have any abnormality or permanent body art (e.g., tattoo), in the opinion of the investigator, would obstruct the ability to observe local reactions at the vaccination site.
- 23. Have had any blood loss >400 mL, e.g., due to donation of blood or blood products or injury, within the 28 days prior to Screening Visit or plan to donate blood or plasma during the trial, starting from Screening Visit and continuously until at least 28 days after be given the last immunization.
- 24. Travel or live in any country or region with a high SARS-CoV-2 infection risk (as defined at Screening Visit) within the 14 days prior to Screening Visit.
- 25. They plan to visit any country or region with a high SARS-CoV-2 infection risk (as defined at Screening Visit), from Screening Visit until 14 days after be given the last immunization.
- 26. Symptoms of COVID-19, e.g., respiratory symptoms, fever, cough, shortness of breath and breathing difficulties.
- 27. Have had contact with confirmed COVID-19 patients or persons tested positive for SARS-CoV-2 within the 30 days prior to Screening Visit.

28. Are vulnerable persons, e.g., soldiers, subjects in detention, CRO or Fosun staffs or their family members.

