#### **Exclusion criteria:**

- 1. Baseline laboratory abnormalities with Grade ≥3 (for hematology abnormalities with Grade ≥2, according to the grading criteria in appendix B) during screening visits, by physical examination and eligibility screening.
- 2. Have had any acute illness, as determined by the investigator, with or without fever, within 72 h prior to the prime vaccination. An acute illness which is nearly resolved with only minor residual symptoms remaining is allowable if, in the opinion of the investigator, the residual symptoms will not compromise their well-being if they participate as trial subjects in the trial, or that will not prevent, limit, or confound the protocol-specified assessments.
- 3. Have a known allergy, hypersensitivity, or intolerance to the planned vaccine for trial including any excipients.

- 4. Used to have a history of hypersensitivity or serious reactions to vaccination.
- 5. Received any vaccination within 4 weeks prior to Visit 1.
- 6. Don't agree to not be vaccinated during the trial, starting from Screening Visit and continuously until 28 days after receiving the last immunization, except emergency vaccination (e.g. rabies vaccine, tetanus vaccine).
- 7. Had administration of any immunoglobulins and/or any blood products within the 3 months prior to Screening Visit.
- 8. Had any serious or life-threatening medical condition (e.g., autoimmune disease, cardiovascular disease) within the past 5 years, which in the opinion of the investigator, could compromise their well-being if they participate as trial subjects in the trial, or that could prevent, limit, or confound the protocol-specified assessments.
- 9. Have any surgery planned during the trial, starting from Screening Visit and continuously until at least 90 days after the last immunization.
- 10. Had any chronic use (more than 14 continuous days) of any systemic medications that affects immune function, including immunosuppressant or other immune-modifying drugs, within 6 months prior to Screening Visit unless in the opinion of the investigator, the medication would not prevent, limit, or confound the protocol-specified assessments or could compromise safety of subjects.
- 11. Had administration of another investigational product including vaccines within 60 days or 5 half-lives (whichever is longer), prior to Screening Visit.
- 12. With known history of AIDS or HIV test positive.
- 13. History of HBV or HCV infection.

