#### **Exclusion criteria:**

- 1. Physical examination and qualifying screening during screening visits, finding baseline laboratory abnormalities  $\geq$ grade 3 (for hematology abnormalities with Grade  $\geq$ 2, according to grading criteria in Appendix B).
- 2. Have had any acute illness, as determined by the investigator, with or without fever, within 72 h prior to the prime vaccination. An acute illness which is nearly resolved with only minor residual symptoms remaining is allowable if, in the opinion of the investigator, the residual symptoms will not compromise their well-being if they participate as trial subjects in the trial, or that could not prevent, limit, or confound the protocol-specified assessments.
- 3. Have a known allergy, hypersensitivity, or intolerance to the planned vaccine for trial including any excipients.
- 4. Used to have a history of hypersensitivity or serious reactions to vaccinations.
- 5. Received any vaccination within 4 weeks prior to Visit 1.
- 6. The subject doesn't agree to avoid vaccination during the trial, starting from Screening Visit and continuously until 28 days after receiving the last immunization, except emergency vaccination (e.g. rabies vaccine, tetanus vaccine).

- 7. Had administration of any immunoglobulins and/or any blood products within the 3 months prior to Screening Visit.
- 8. Had any serious or life-threatening medical condition (e.g., autoimmune disease, cardiovascular disease) within the past 5 years, which in the opinion of the investigator, could compromise their well-being if they participate as trial subjects in the trial, or that could prevent, limit, or confound the protocol-specified assessments.
- 9. Have any surgery planned during the trial, starting from Screening Visit and continuously until at least 90 days after the last immunization.
- 10. Had any chronic use (more than 14 continuous days) of any systemic medications, including immunosuppressant or other immune-modifying drugs, within 6 months prior to Screening Visit unless in the opinion of the investigator, the medication would not prevent, limit, or confound the protocol-specified assessments or could compromise safety of subjects.
- 11. Had administration of another investigational product including vaccines within 60 days or 5 half-lives (whichever is longer), prior to Screening Visit.
- 12. With known history of AIDS or HIV test positive.
- 13. Have infection history of HBV or HCV.

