# 9.1.2 Demographics, medical history, travel history, prior/concomitant medications/vaccinations, and blood donation

Demographic information, to be obtained at Screening Visit, will include age (date of birth), sex, race, and ethnicity as provided by the subject. See Section 6.1 for more details about the enrollment.

Medical history will also be collected at Screening Visit and at Visit 1 (Day 1) pre-vaccination and will include any medical history that may be relevant to subject eligibility for trial participation such as prior vaccinations, concomitant medications, and previous and ongoing illnesses or injuries. Relevant medical history can also include any medical history that contributes to the understanding of an AE that occurs during trial participation, if it represents an exacerbation of an underlying disease/preexisting problem.

Medical occurrences before administration of the first dose of investigational vaccine/placebo are considered medical history.

Travel history to SARS-CoV-2 endemic countries and SARS-CoV-2 endemic regions of China within 2 weeks prior to screening will be collected at Screening Visit. Travel history to SARS-CoV-2 endemic countries and SARS-CoV-2 endemic regions of China will be collected at each visit.

Ask the subject's medical history, record the following medication of the subject: 4 weeks within the vaccincation, long-term use of systemic medication affecting the immune function within 6 months, immunoglobulin and/or blood products within 3 months, take another kind of study drug (including vaccine) within 60 days or five half-life (will be subject to a long time). And all medications, vaccines and blood products taken or received by the subjects within 1 monthprior to the start of the trial are to be recorded on the source document (patient record) and entered on the Prior and Concomitant Medications eCRF. The use of antipyretics and/or analgesic medications within 24 hours prior to vaccination must be identified and the reason for their use (prophylaxis versus treatment) must be described in the source documents and the eCRF.

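### Three eligibility passages are inverted or contradict each other: the adult residual-illness allowance, the safety limb of the chronic-medication waiver, and the scope of the chronic-medication exclusion

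*Protocol*

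**What the plan says.** **Residual illness.** Adult exclusion 1, in Protocol Sections 2.0 and 7.1, bars acute illness in the 72 hours before the first dose but makes an exception for one that has nearly resolved. The exception applies if "the residual symptoms will not compromise their well-being if they participate as trial subjects in the trial, or that could prevent, limit, or confound" the assessments. Elderly exclusion 2 has the same exception with a negation: "or that will not prevent, limit, or confound the protocol-specified assessments" in Section 2.0 and "or that could not prevent, limit, or confound the protocol-specified assessments" in Section 7.2. Adult exclusion 7 uses the phrase "or that could prevent, limit, or confound the protocol-specified assessments" as a reason to keep a subject out.

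**Waiver for chronic medication.** Adult exclusion 9, elderly exclusion 10 (each in Section 2.0 and again in 7.1 or 7.2) and the prohibited-medication list in Section 9.1.2 all let the investigator waive the exclusion if the drug "would not prevent, limit, or confound the protocol-specified assessments or could compromise safety of subjects".

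**Scope of the same exclusion.** Section 2.0, for both age groups, covers "any systemic medications that affects immune function, including immunosuppressant or other immune-modifying drugs", and the Section 9.1.2 list has the same limit. Sections 7.1 and 7.2 cover chronic use "of any systemic medications, including immunosuppressant or other immune-modifying drugs, within 6 months prior to Screening Visit". The Section 9.1.2 list cites Section 7.0 as its source.

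**What is recorded.** Section 9.1.2 asks for "long-term use of systemic medication affecting the immune function within 6 months", and for all medications over one month before the start of the trial.

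**Where eligibility enters the analysis.** Protocol Section 13.1.1 counts meeting an exclusion criterion as a major violation that removes a subject from the PPS. SAP Section 6 removes only violations of major criteria and does not list them. Safety is analysed in the Safety Set.

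**The concern.** These are operative rules that a site applies to each volunteer. For adults, the text offers interference with the assessments as a qualifying condition in one criterion and as a disqualifying one in another. For medication, two texts of the same exclusion admit different people. A volunteer on a routine long-term drug that does not affect immune function needs no waiver under Section 2.0 but needs one under 7.1 or 7.2. A systemic hormonal contraceptive, if used to satisfy adult inclusion 11, would be one example; the protocol does not say which methods count.

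The stake for the analysis is the PPS. If a subject on such a drug was enrolled without a waiver, the blinded review would have to call that a major violation on one text and no violation on the other. There is a second, weaker stake. Headache, fatigue, myalgia and nausea are solicited from the day of vaccination, so a residual symptom at entry might be recorded as a reaction.

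**Working it through.** The point is about wording, so the check sets the passages side by side. The only design figure, in Protocol Section 13.3, reproduces and is not affected: 1 − 0.92^24 = 0.865, the stated 86.5%.

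**Step 1. Residual illness.** Let W mean the symptoms will not compromise well-being and C mean they could interfere with the assessments. As written, the adult rule allows W or C, and the elderly rule allows W or not-C.

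| Residual symptoms | Adult, literal | Elderly, literal | Adult, *or* read as *and* | Elderly, *or* read as *and* |
|---|---|---|---|---|
| Harmless, do not interfere | allowed | allowed | barred | allowed |
| Harmless, interfere | allowed | allowed | allowed | barred |
| Harmful, interfere | allowed | barred | barred | barred |
| Harmful, do not interfere | barred | allowed | barred | barred |

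The adult and elderly rules differ on either reading. With *and*, the adult rule admits only the interfering symptoms. With *or*, it admits harmful symptoms provided that they interfere. Neither adult reading fits adult exclusion 7, which excludes a condition within the past five years that could interfere.

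**Step 2. Waiver.** Let N mean the drug would not interfere with the assessments and S mean it could compromise safety. The text waives N or S.

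| Drug | Waived as written? |
|---|---|
| Does not interfere, safe | yes |
| Does not interfere, could compromise safety | yes |
| Interferes, could compromise safety | yes |
| Interferes, safe | no |

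The only drug refused a waiver is one that interferes and is safe. The assessment limb reads as a waiver condition should. The inversion is in the safety limb.

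**Step 3. Scope.**

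| Place | Scope |
|---|---|
| Section 2.0, adult exclusion 9 | affects immune function |
| Section 2.0, elderly exclusion 10 | affects immune function |
| Section 7.1, exclusion 9 | any systemic medication |
| Section 7.2, exclusion 10 | any systemic medication |
| Section 9.1.2 list, citing Section 7.0 | affects immune function |

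The split is three against two. It is not simply summary against body, because Section 9.1.2 sides with the summary against the section that it cites.

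**Step 4. Can the wider scope be verified?** The exclusion looks back six months. Non-immune drugs are expressly recorded for one month. Ignoring the small difference between Screening and trial start as reference points, 6 − 1 = 5 months are not expressly covered. Current long-term use falls within the one-month record. What can be missed is a non-immune drug that was stopped between one and six months earlier. Section 9.1.2 also collects medication linked to significant resolved conditions, so some of these would be caught.

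**Step 5. Primary endpoint.** Protocol Section 10.1.1 counts an event present before the first dose as treatment-emergent only if it worsened. SAP Section 7.6.1 presents solicited reactions as treatment-emergent events. SAP Section 7.1.2, however, implements the definition by start date: an event on the day of the first dose, or with no start date, counts. Diaries are issued after vaccination (Protocol Section 9.3.4). Neither document says how to date a solicited symptom already present on Day 1 and then entered in the diary. If one such subject were counted, that arm's rate would move by 1/24 = 4.2 percentage points. The documents give no rate at which this would happen.

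**The case against.** The strongest reply is that these are drafting slips with little practical reach. Much of that stands.

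- *Adult illness is barred elsewhere.* A subject must meet no exclusion criterion (Protocol Section 9.1.10), so exclusion 7 can stop what exclusion 1 lets through. Exclusion 26 and the 37.0 °C limit also bar respiratory symptoms and fever. This reduces the harm, but it leaves two criteria in conflict.
- *The elderly text is loose too.* Its limbs are joined by *or*, so taken literally a harmless but interfering symptom passes there as well. That is correct, and the connector should be settled in the same edit.
- *The PPS.* A reader might infer that PPS membership cannot be checked at all. The documents do not support that. The doubt concerns these criteria, current drugs are recorded, and immune-affecting drugs, the ones most relevant to immunogenicity, have a six-month history. Day 7 and Day 21 immunogenicity is also analysed in the TVC.
- *The primary endpoint.* A reader might infer that pre-existing symptoms inflate solicited reactions or dilute the difference between vaccine and placebo. The treatment-emergent definition removes unworsened events, blinded 1:1:1 allocation would be expected to spread any background evenly, and SAP Section 7.1 plans no formal testing. A medication waiver does not bring symptoms into that endpoint either.

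None of this answers the scope contradiction or the inverted safety limb.

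**Conclusion.** The point holds as a defect of three eligibility passages: the adult residual-illness allowance, the safety limb of the waiver, and the scope of the chronic-medication exclusion. The scope and waiver faults affect both age groups; the missing negation affects adults only. The consequence that follows directly is that enrolment, and the protocol's PPS rule, depend on which text governs.

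No numerical size can be given, because it would need rates of residual illness and of long-term medication that the documents do not contain. The PPS consequence reaches immunogenicity only. An effect on the primary safety endpoint is possible and not shown; it rests on the unclear handling of diary symptoms already present on Day 1, and the 4.2 points per subject apply only if such a symptom is counted. The verdict takes the criteria as they would be read literally by a site. It does not say which clinical rule is the right one.

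**What to change.** 1. Reconcile adult exclusion 1 (Sections 2.0 and 7.1) with elderly exclusion 2 (Sections 2.0 and 7.2) and with adult exclusion 7, and settle whether the two limbs must both hold or either suffices.
2. Correct the logic of the waiver's safety limb in all five places, so that a risk to safety is not a ground for exemption.
3. Choose one scope for the chronic-medication exclusion and use it in Sections 2.0, 7.1, 7.2 and 9.1.2. The choice is the sponsor's.
4. If the wider scope is kept, have Section 9.1.2 record all systemic medication over the same six months.
5. Add a sentence to SAP Section 7.1.2 on how a solicited symptom already present before the first dose is dated and counted.

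The cost is the wording of a few criteria, one sentence in the SAP and, only under the wider scope, one extended medication-history field. No sample size or analysis method changes.
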